## **7 *Study execution***

### **7.1 *Patient identification and consenting***

Patients are identified in the Department of Urology, Turku University Hospital. If the patient meets inclusion criteria, he will be informed of the study verbally and with the written information.

After adequate consideration of time, if the patients agree to participate in the study, signed informed consent is obtained. After this imaging studies are arranged within 2 weeks.

### **7.2 *Laboratory sampling***

In addition to imaging studies, besides routine clinical blood samples, an extra blood and urine sample are collected simultaneously for future molecular genetic studies exploring possible prognostic biomarkers for disseminated/metastasized PC.

### **7.3 *Planar bone scintigraphy***

Planar bone scintigraphy will be performed as a part of routine clinical evaluation protocol. The subjects will be positioned supine on a Discovery NM/CT 670 CZT, a digital SPECT/CT scanner (General Electric Healthcare). The scanner includes a dual-detector, free-geometry integrated nuclear imaging camera with the advanced digital CZT detector technology combined with the high-performance Optima CT540 subsystem. Whole-body planar images will be scanned from the anterior and posterior views three hours after the intravenous injection of 670 MBq of  $^{99m}\text{Tc}$ -HMDP. A wide-energy high-resolution (WEHR) collimator, a scan speed of 13 cm/min, a zoom of 1.0 and a matrix size of 256 x 1024 are used in the scintigraphy.

### **7.4 *Computer tomography***

Computed tomography of the thorax, abdomen and pelvis will be performed as a part of routine clinical evaluation protocol. The imaging will be done with contrast agent if there are no clinical contraindications for the use of contrast agent.

### **7.5 *SPECT-CT***

SPECT/CT imaging will be carried out after acquisition of the planar images with the same scanner. Three bed positions of SPECT data will be acquired from the top of the head to mid femoral level using WEHR collimators. A non-circular orbit, 60 views with 15-s scanning time per view will be acquired during 180 degrees of rotation. A 128 x 128 matrix size, a zoom of 1.0 and 15% photopeak and lower scatter energy windows are used. After SPECT a CT topogram and a low-dose tomogram with a modulated mAs (noise index ~ 70), 120 kVp, a pitch of 1.35 and a 2.5-mm slice thickness are scanned. The co-registration of SPECT and CT data is verified after which

the SPECT images are reconstructed using modern iterative ordered subsets expectation (OSEM) reconstruction algorithm from General Electric or Hermes Medical Solutions, which includes, e.g., 10 iterations and 5 subsets and attenuation, collimator and scatter corrections.

## **7.6 MRI**

Magnetic resonance imaging examination will be performed using a 1.5T (Philips 1.5T Ingenia, Best, Netherlands and/or Siemens 1.5T Aera/Avant, Erlangen, Germany) or 3T (Philips 3T Ingenia, Best, Netherlands and/or Siemens 3T Skyra fit, Erlangen, German) MR system. The body matrix coil in combination with a spinal coil will be used for image acquisition. T1-weighted anatomic imaging, STIR fat suppressed images and DWI will be performed in axial and coronal directions. DWI will be obtained with single-shot 2D spin-echo echo-planar imaging. The total scan time will be approximately 25-35 minutes.

## **7.7 PSMA-PET**

F-PSMA-1007 tracer is manufactured by MAP Medical Technologies Oy (Helsinki, Finland). This radiolabeled tracer is targeting the prostate specific membrane antigen (PSMA). The solution is developed DKFZ and ABX companies and it is used for imaging studies with positron emission tomography (PET) (29.)

F -PSMA-1007 is produced by radiolabelling with fluorine-18 (T1/2= 109,77 min) produced by irradiating oxygen-18. Administration of the formulated solution is done shortly (<10h) after production after quality control and release of the drug product by a Qualified Person. The process has been tested in three consecutive validation runs, showing consistent results. The results show that the solution met the requirements for sterility and bacterial endotoxins according to the European pharmacopoeia, confirming an acceptable manufacturing process from a microbiological point of view. Process verification and tests for microbiological purity is performed for all new batches of precursors and synthesis equipment before the manufacture

The PET/CT studies are carried out with digital PET/CT scanner: Discovery MI (General Electric Medical Systems, Milwaukee, WI, USA). It has combined PET/CT-scanners with a 128-slice CT and a 3D PET imaging capability. The PET imaging field of view (FOV) is 70 cm in diameter and 15.7 cm in axial length. To obtain attenuation correction for 511 keV photon distribution,

transmission scan is performed using a low-dose (noise index 25, automatic 3D current modulation, max 64 mAs and 120 kVp) CT protocol.

The patients receive intravenous injection of approximately 200-300MBq (3 MB/kg) of F-PSMA-1007 diluted in 3-5 ml of saline as a 60-sec bolus which will be promptly flushed with saline. Before data acquisition patients will be asked to void. A static emission scan will be acquired 60-min from tracer injection over whole body. The sinogram data will be corrected for deadtime, decay and photon attenuation and reconstructed in a 256x256 matrix. Image reconstruction follows a fully 3D maximum likelihood ordered subsets expectation maximization (ML-OSEM) algorithm incorporating random and scatter correction with two iterations and 28 subsets. The final in-plane FWHM (full-width half-maximum) of the systems is < 6 mm.

### **7.8 Definition and recording of imaging findings**

Imaging modalities will be read blindly without the knowledge of results of the other imaging modalities. Readers will only know that a patient has prostate cancer with high risk for metastases. All imaging data will be analyzed visually with classifying lesions as normal, equivocal or metastatic. Number and type of lesion will be recorded for each of following body parts: head, upper extremity, spine, rib and sternum, pelvis, lower extremity.

Lesions will be graded as highly suspicious for being metastases, equivocal or benign. On bone scans, lesions will be categorized as benign when they were located around joints, hot osteophytes, vertically involving several ribs (suggesting fracture), H-shaped pelvic abnormal, bursitis, avulsion injury, tendinitis. The vertebral lesions were considered as highly suspicious when they involved posterior aspect, pedicle or the whole vertebral body. A lesion will be considered as highly suspicious on MRI if a focal or diffusion low signal intensity (SI) was present on T1wi with the corresponding intermediate or high SI on STIR and/or restricted diffusion on DWI. Typical benign lesions and/or sclerosis will be interpreted according to previously published criteria. Trace images (geometric mean of 3 diffusion directions) will be evaluated visually in conjunction with anatomical T1wi and STIR. No quantitative cut-off values were used for DWI.

Anatomical localization of the potential tumor deposits will be confirmed by aligning the whole-body PET images with the corresponding CT images using Volumetrix™ hybrid imaging

software of the General Electric AWTM workstation where all visual and quantitative analyses of tracer uptake will be performed. Concurrent diagnostic evaluation of CT scans is made with Advantage Workstation version 4.6 for advanced processing. The findings on PET/CT whole-body images will be related to all previous clinical and imaging data and any new information likely to change patient's further treatment will be confirmed by other methods such as additional imaging studies.

Regions of interests (ROIs) will be placed in the suspicious tumor lesion as seen in the co-registered CT. Tracer accumulation is measured as Standardized Uptake Value (SUV), which is the ratio of measured radioactivity concentration to the estimated body tracer concentration, assuming a uniform distribution throughout the entire body volume.

The bone, nodal and extra nodal findings will be compared on patient-, region- and lesion-level. In the region-based analysis for bone metastasis, the skeleton was divided into five regions: head, thorax and ribs, spine, pelvis and limbs. In the lesion-based analysis, only lesions which were highly suspicious or equivocal on at least one imaging modality were included. In addition, maximum of 5 lesions with the highest agreement between modalities per anatomical location (5 locations as defined in the region-based analysis) were included in the lesion-based analysis.

A detailed data collection sheet is applied prospectively for recording separately each individual imaging study results of equivocal, benign and malignant lesion/s.

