## **6 Study endpoints, statistical considerations, and sample size**

### **6.1 Study endpoints**

The primary endpoint of the study is

1. Comparison of AUC values of  $^{18}\text{F}$ -PSMA-1007 to  $^{99\text{m}}\text{Tc}$ -HMDP in pessimistic, patient-based analysis detecting of bone metastases in the initial staging of high-risk PC patients.

The secondary end-points include

1. The sensitivity, specificity, accuracy and AUC value of  $^{18}\text{F}$ -PSMA-1007, whole-body MRI including DWI,  $^{99\text{m}}\text{Tc}$ -HMDP SPECT-CT,  $^{99\text{m}}\text{Tc}$ -HMDP planar bone scintigraphy and contrast enhanced CT detecting bone metastases in the initial staging of high-risk PC patients.
2. The sensitivity, specificity, accuracy and AUC value of  $^{18}\text{F}$ -PSMA-1007, whole-body MRI including DWI,  $^{99\text{m}}\text{Tc}$ -HMDP SPECT-CT,  $^{99\text{m}}\text{Tc}$ -MDP planar bone scintigraphy and contrast enhanced CT detecting lymph node metastases in the initial staging of high-risk PC patients
3. The sensitivity, specificity, accuracy and AUC value of  $^{18}\text{F}$ -PSMA-1007, whole-body MRI including DWI,  $^{99\text{m}}\text{Tc}$ -HMDP SPECT-CT,  $^{99\text{m}}\text{Tc}$ -HMDP planar bone scintigraphy and contrast enhanced CT detecting soft tissue metastases (excluding pelvic lymph node metastases) in the initial staging of high-risk PC patients
4. The effect of staging on clinical treatment-decisions

As in some cases the definition of a metastatic lesion is not confirmed with absolute certainty (e.g. with histological diagnosis) the final diagnosis concerning the metastatic status will be determined during follow up consisting of appropriate imaging modality and follow-up information from other parameters, especially PSA levels.

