## **6.2 *Statistical considerations and sample size***

The power calculations are made according to our primary endpoint and on the basis of previously published work, the SKELETA trial. To be able to detect the 19% difference using a two-tailed test with a power of 80% at a significance level of 0.05 in a 2:1 ratio of sample sizes in negative/positive groups, 48 cases and 24 positive cases are required. Together 72 patients will be the sample size and taking into account possible dropouts, permission for 80 patients will be applied for Ethical Committee.

Equivocal findings of the imaging modalities will be classified either as suggestive for metastases (“pessimistic analysis”) or suggestive for non-metastatic origin (“optimistic analysis”). Sensitivity and specificity values of patient-, region- and lesion-based analyses will be compared using McNemar test and two-sided p-values will be calculated. In region-based analysis, diagnostic accuracy values for the detection of bone metastases (sensitivity, specificity, accuracy and AUC) will be calculated from all ROIs which will be pooled into one group. Moreover, receiver operation characteristic curves (ROC) analysis will be performed using 60 000 bootstraps to account for within-patient correlations. Area under the curve (AUC) values will be calculated using the trapezoid rule and compared using a method described by Hanley and McNeil two-sided p-values will be calculated (28). Bootstrap samples will be constructed by stratifying patients based on overall cancer level (cancer present or not) and drawing patients as the independent units with replacement from these groups (cancer present or not). P-values smaller than 0.05 will be considered statistically significant.

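### Where a location holds more than five eligible lesions, the secondary lesion-based analysis keeps those on which the modalities agree most, biasing its differences between modalities toward zero

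*Protocol*

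**What the plan says.** Section 7.8 states the purpose: "The bone, nodal and extra nodal findings will be compared on patient-, region- and lesion-level". It then sets two filters for the lesion-based analysis.

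- Eligibility: "only lesions which were highly suspicious or equivocal on at least one imaging modality were included".
- Cap: a "maximum of 5 lesions with the highest agreement between modalities per anatomical location", where the locations are the five of the region-based analysis ("the skeleton was divided into five regions: head, thorax and ribs, spine, pelvis and limbs").

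Section 6.2 gives the test: "Sensitivity and specificity values of patient-, region- and lesion-based analyses will be compared using McNemar test and two-sided p-values will be calculated". The threshold is 0.05.

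The protocol nowhere replaces the agreement ranking with a neutral one, defines agreement, or adds an uncapped lesion analysis. It does not say whether the cap applies per patient. The primary endpoint in Section 6.1 is the AUC comparison "in pessimistic, patient-based analysis detecting of bone metastases in the initial staging of high-risk PC patients".

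**The concern.** The cap selects lesions on the quantity being compared. A lesion seen by one modality and missed by another carries the information about their difference, and McNemar's statistic is built from such lesions alone. Ranking by agreement puts them last in the queue, so once a location has more lesions than places, they tend to be lost first. The weaker scan's misses leave the data set and its sensitivity drifts toward that of the better scan. More patients do not cure this, because it is bias and not noise.

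A second, separate problem lies in the eligibility filter. A benign focus that no scan flagged never enters. In the pessimistic classification, a true negative for one scan therefore exists only where another scan raised a false alarm. Specificity computed on that set describes the panel of scans, not the single modality.

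At stake is a secondary layer of the results: whether the trial can describe how the modalities differ lesion by lesion in patients with extensive disease.

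**Working it through.** **Inputs from the protocol.** Cap of 5 per location, ranked by agreement; eligibility if flagged on at least one modality; McNemar test (Sections 7.8 and 6.2). The protocol states no lesion-level figure, so there is nothing to reproduce.

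**Inputs assumed.** Lesion-level sensitivities, correlation between modalities and lesions per location are not given. Reads were simulated as correlated probit variables with latent correlation 0.3. Only metastatic lesions flagged by at least one of five modalities were kept. Agreement was taken as the size of the majority among the five reads. The difference is best minus weakest modality.

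**Setting A: sensitivities 0.85/0.80/0.75/0.65/0.60.**

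| Eligible lesions in the location | All lesions | 5 with highest agreement | 5 at random |
|---|---|---|---|
| 5 | 0.25 | 0.25 | 0.25 |
| 6 | 0.25 | 0.21–0.22 | 0.25 |
| 10 | 0.25 | 0.12 | 0.25 |
| 15 | 0.25 | 0.05 | 0.26 |
| 20 | 0.25 | 0.02 | 0.26 |

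At 10 lesions the weakest modality's sensitivity rises from 0.61 to 0.82, and best-versus-weakest discordance falls from 0.38 to 0.18. When the latent correlation is varied from 0.1 to 0.5, the capped difference is 0.21–0.22 at 6 lesions, 0.09–0.15 at 10, 0.02–0.09 at 15 and 0.004–0.04 at 20.

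**Setting B: sensitivities 0.90/0.50/0.40/0.30/0.30.** At 10 lesions the difference moves only from 0.63 to 0.56. The best modality's sensitivity falls slightly (0.947 to 0.934). Under a majority definition, a lesion seen by one scan alone (four of five agree) outranks a three-to-two split, so some lesions seen only by the best scan are kept.

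**Cap or criterion?** The random cap of five leaves the difference unchanged within simulation error. The agreement criterion causes the bias; the cap does not.

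**Pooling over locations.** Let w be the share of retained metastatic lesions that come from locations above the cap. Taking all such locations at 10 lesions in Setting A:

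pooled difference = (1 − w) × 0.25 + w × 0.12

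- w = 0.25: 0.1875 + 0.03 = 0.22
- w = 0.50: 0.125 + 0.06 = 0.19
- w = 0.75: 0.0625 + 0.09 = 0.15

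The protocol gives no basis for choosing w.

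**Specificity under the eligibility filter, before any cap.** For modality A with true specificity Sp among benign foci, in the pessimistic classification:

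apparent specificity = 1 − (1 − Sp) / P(at least one modality flags the focus)

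Assume Sp = 0.90 and independent false alarms.

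- One comparator with specificity 0.85: P = 1 − 0.90 × 0.85 = 0.235; apparent specificity = 1 − 0.10/0.235 = 0.57.
- Four comparators, three at 0.90 and one at 0.85: P = 1 − 0.90⁴ × 0.85 = 0.442; apparent specificity = 1 − 0.10/0.442 = 0.77.

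The same scan scores 0.57 or 0.77 according to which other scans are in the study.

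**The case against.** **The main comparison is safe.** This stands. The primary endpoint and the sample size are patient-based, Section 6.2 pools all ROIs in the region-based analysis, and Section 6.1 names lesion level in no endpoint. A bias toward no difference also cannot manufacture superiority for PSMA-PET.

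**The effect is conditional.** This stands too. A reader might infer that the rule strips out disagreement throughout the lesion analysis. It does not: every discordant lesion is kept wherever a location has five or fewer. Section 6.2 plans 24 positive patients, and mainly those with many lesions in one location are affected.

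**Sensitivities are not all inflated.** Correct: Setting B shows the best modality's falling slightly. What both settings show is a rise for the weakest modality and a smaller difference.

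**The cap has a purpose.** Limiting the weight of patients with many lesions is reasonable, but a neutral cap does that without the bias. Agreement may also ease matching of lesions across blinded reads. Section 7.8 does not give that reason, and excluding lesions seen on only some scans would exclude the differences under study.

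**Two further readings go beyond the text.** One might conclude that a lesion-level AUC is planned and must be withdrawn. Section 6.2 ties AUC explicitly to the region-based analysis, and for lesions names only sensitivity and specificity. One might also read the cap as study-wide (5 × 5 = 25 lesions in all), which would make the bias worse. The text leaves the unit open, and per patient is the natural reading.

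**Conclusion.** The lesion selection rule is wrong as written and should be fixed. Above five eligible lesions in a location it selects on concordance, pulls lesion-level differences toward zero and inflates the weakest modality's sensitivity. The direction held in every simulated setting above the cap. The size depends on assumed sensitivities, correlation, lesion counts and the undefined meaning of agreement: at 10 lesions, from 0.25 to 0.12 in one setting and from 0.63 to 0.56 in another. The near-disappearance of the difference at 20 lesions applies to such locations in Setting A and is not an estimate for the whole trial.

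A null lesion-level McNemar result could not be read as equivalence where the cap operates. The primary endpoint, the region-based analysis and locations with five or fewer lesions are not affected.

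The specificity point holds independently of the cap: as constructed, lesion-level specificity should not be interpreted as a property of a modality.

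**What to change.** 1. In Section 7.8, strike the words that rank lesions by agreement. Then choose one of two routes.
   - Keep the cap, state that it applies per patient and location, and select the five at random (recorded seed) or by another rule that does not use the modality reads.
   - Analyse all eligible lesions, with inference clustered by patient. The patient-level bootstrap that Section 6.2 already describes for the ROC analysis could be extended to this.
2. In Section 6.2, drop the lesion-level test of specificity. Report instead the detection rate (share of confirmed metastatic lesions in the pooled list that the modality flagged) and the positive predictive value (share of the modality's flagged lesions that were confirmed). The latter uses only the modality's own flags.

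**Cost.** About one sentence in each section, and no additional scans. The real work is matching lesions across blinded reads. Section 7.8 provides for recording findings separately for each imaging study, but does not promise a lesion-by-lesion list matched across modalities. Both routes need one, and it takes most effort in extensive disease. The random cap limits the analysis to five lesions per location but still needs a matched list to draw from.

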## **8 Duration of the study**

Enrollment of the patients to the study will start as soon as the Research Ethics Approval has been obtained and hospital permissions is available. The enrollment is estimated to spring 2018. The accrual period will end as the accrual target is fulfilled. This is estimated to take 18 months. For individual patients the study is concluded after the imaging studies with conclusive findings are

available. In the case of inconclusive imaging findings, follow-up is arranged for appropriate time period until the imaging lesion status is confirmed.

## **9 Administrative considerations**

The trial will be conducted in compliance with the "Principles of Good Clinical Practice" (ICH-GCP). The investigator is responsible that the trial is carried out in accordance with the Declaration of Helsinki in the revised version of Somerset West, South Africa 1996 and the "Principles of Good Clinical Practice" (ICH-GCP), 1997.

### ***9.1 Ethical review***

The Principal Investigator (PI) is responsible for obtaining approval of the EC for the study protocol including its appendices. The PI shall file all correspondence with the EC in the Investigator's Study File.

### ***9.2 Information of the study subject***

Every patient will be informed about the study details in accordance with the enclosed patient information sheet. The patient is informed both in writing information sheet and verbally by the physician. The patient must have the opportunity to decide whether or not to participate in the clinical trial and this decision will not affect the clinical treatment. Both the informing physician and the patient must sign a declaration of consent. The patient will retain a copy of the declaration. The declarations of consent are part of the patient file and will be retained with this.

## **10 Quality assurance**

### ***10.1 Study personnel and training***

The clinical investigators and research staff (research coordinator and research nurse) at Department of Urology are experienced in conducting various types of clinical trials including imaging studies in uro-oncology. This team will take care of study subject identification, information and consenting as well as clinical treatment of the individuals. The technical and other supporting personnel of Department of Clinical Physiology and Nuclear Medicine, and Department of Diagnostic

Radiology is well experienced in performing  $^{99m}\text{Tc}$ -MDP BS, CT, and MRI studies. In the beginning of the study all investigators will be informed on the practical implementation of the protocol in a separate meeting. They will be informed on the rationale of the study and possible clinical implications as well.

